8 **PFS (days)** = Date of event or Censor date – treatment start date + 1

9 Patients who have not progressed or died at the time of analysis will be censored at the time of the latest date of assessment from their last evaluable assessment. However, if the patient progresses or dies after 2 or more missed visits, the patient will be censored at the time of the latest evaluable assessment prior to the 2 missed visits. If the patient has no evaluable visits or does not have baseline data, he/she will be censored at Day 1 unless he/she dies within 2 visits of baseline, in which case the date of death is the event date.

10 **OS:** Defined as the time from the first date of treatment until death due to any cause.

11 **OS (days)** = Death date or Censor date - treatment start date + 1

12 Any patient not known to have died at the time of analysis will be censored based on the last recorded date on which the patient was known to be alive.

13 Lung cancer mortality (NSCLC-related death): Defined as the time from the date of treatment start until death due to lung cancer.

Time to NSCLC-related deaths (days) = NSCLC-related death date or Censor date - treatment start date + 1

Any patient not known to have died due to lung cancer will be censored based on the last recorded date on which the patient was known to be alive or died due to reason other than lung cancer.

14 **ORR:** Based on Investigator-assessed response to treatment of CR and PR, per RECIST1.1.

15 **DoR:** Defined as the time from the date of first documented response per RECIST1.1 until the first date of documented progression per RECIST1.1 or death in the absence of disease progression.

- 16 DoR (days) = Date of PFS event or censoring – Date of first response + 1
- 17 The end of response should coincide with the date of progression or death from any cause used for the PFS endpoint. If a patient does not progress following a response, then the patients' DoR will be censored at the PFS censoring time. DoR will not be defined for those patients who do not have a documented response.

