#### **3.3.1 Progression-Free Survival**

Progression-free survival is defined as the time from the date of first dose of durvalumab until the date of objective disease progression or death (by any cause in the absence of progression) regardless of whether the patient discontinues durvalumab or receives another anticancer therapy prior to progression.

- $PFS \text{ (days)} = (\text{date of PFS event or censoring}) - (\text{date of first dose of durvalumab}) + 1$ .

Patients who have not progressed or died at the time of analysis will be censored at the date of their last evaluable tumor assessment (ie, this doesn't include NE or missing value).

If the patient progresses or dies after 2 or more missed visits, the patient will be censored at the date of the latest evaluable assessment prior to the missed visits.

If the patient has no evaluable visits or does not have baseline data, he/she will be censored at Day 1 unless he/she dies within 2 visits of baseline, in which case the date of death is the event date.

Given the scheduled visit assessment scheme (i.e. eight-weekly for the first 48 weeks then twelve-weekly thereafter) the definition of 2 missed visits will change.

1. If the previous RECIST assessment is baseline then two missing visits will equate to 17 weeks since the previous RECIST assessment, allowing for a late visit (i.e.  $2 \times 8$  weeks + 1 week for a late assessment = 17 weeks).
2. If the previous RECIST assessment is post baseline and less than study day 274 (i.e. week 39) then two missing visits will equate to 18 weeks since the previous RECIST assessment, allowing for early and late visits (i.e.  $2 \times 8$  weeks + 1 week for an early assessment + 1 week for a late assessment = 18 weeks).
3. If the two missed visits occur over the period when the scheduled frequency of RECIST assessments changes from eight-weekly to twelve-weekly this will equate to 22 weeks (i.e. take the average of 8 and 12 weeks which gives 10 weeks and then apply same rationale, hence  $2 \times 10$  weeks + 1 week for an early assessment + 1 week for a late assessment = 22 weeks). The time period for the previous RECIST assessment will be from study days 274 to 344 (i.e. week 39 to week 49).
4. From week 49 onwards (when the scheduling changes to twelve-weekly assessments), two missing visits will equate to 26 weeks (i.e.  $2 \times 12$  weeks + 1 week for an early assessment + 1 week for a late assessment = 26 weeks).

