### **3.3.5 Duration of Response**

For patients who are classified as responders (see Section 3.3.3), the DoR is defined as the time from the date of first documented response (which is subsequently confirmed) until the first date of documented progression or death in the absence of disease progression

- DoR = (date of PFS event or censoring) – (date of start of response) +1

The date of the end of response will coincide with the date of disease progression or death from any cause used for the PFS endpoint (see Section 3.3.1). If a patient does not progress following a response, then their DoR will be censored at the date used in the PFS censoring. The date of

the initial response will be defined as the latest of the dates contributing toward the first visit response of CR or PR that was subsequently confirmed. DoR will not be defined for those patients who do not have documented confirmed response.

DoR will also be obtained using the algorithm described above for the RECIST 1.1 site Investigator tumor data

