## **4.4 Analysis of Secondary Efficacy Endpoints**

### **4.4.1 Progression-Free Survival**

Kaplan-Meier plots and descriptive statistics will be provided for PFS. Summary statistics will include lower and upper quartile and median PFS, PFS6 (Day 180) and PFS12 (Day 365).

Summaries of the number (%) of patients experiencing a PFS event (overall and also at Month 6 and Month 12) and the type of event (disease progression or death) will be provided.

All summary statistics will be presented with the appropriate 95% CI.

If necessary, a sensitivity analysis will be conducted to assess the potential impact of COVID-19 related deaths on PFS. That is, patients who had a PFS event due to death where the primary or secondary cause of death was COVID-19 infection or COVID-19 infection was reported as a fatal AE, will be censored at the last evaluable RECIST 1.1 assessment prior to COVID-19 infection related death.

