### **4.4.4 Duration of Response**

A Kaplan-Meier plot and descriptive statistics will be provided for the DoR and the respective

Time to onset of first response for patients in the SAF who had responded to treatment (see Section 3.3.5). Summary statistics will include: lower and upper quartile and median DoR with appropriate 95% CIs.

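### SAP 3.3.1: the day range of the 22-week missed-visit rule for PFS also covers the Week 48 scan, where the SAP's own formula gives 26 weeks

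*SAP*

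**What the plan says.** Protocol Table 1 and SAP 3.1 schedule tumor scans from first dose at Weeks 8, 16, 24, 32, 40 and 48, then at Weeks 60, 72, 84 and so on, each with a window of one week either side.

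Protocol 9.4 sets the censoring principle: "if the patient progresses or dies after 2 or more missed visits, the patient will be censored" at the last evaluable assessment before the gap. It gives no week counts. SAP 3.3.1 repeats the principle and supplies four thresholds:

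- **Rule 1**, previous assessment is baseline: 17 weeks.
- **Rule 2**, previous assessment post baseline and before Day 274: 18 weeks.
- **Rule 3**, 22 weeks. The condition is "If the two missed visits occur over the period when the scheduled frequency of RECIST assessments changes from eight-weekly to twelve-weekly". The derivation is "take the average of 8 and 12 weeks which gives 10 weeks and then apply same rationale". The range is "The time period for the previous RECIST assessment will be from study days 274 to 344 (i.e. week 39 to week 49".
- **Rule 4**: "From week 49 onwards (when the scheduling changes to twelve-weekly assessments), two missing visits will equate to 26 weeks".

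For reporting, SAP 4.4.1 states "Summary statistics will include lower and upper quartile and median PFS", and SAP 4.4.4 plans "lower and upper quartile and median DoR with appropriate 95% CIs". Under SAP 3.3.5 the end of response "will coincide with the date of disease progression or death from any cause used for the PFS endpoint", so duration of response (DoR) inherits whatever PFS does.

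**The concern.** Rule 3 gives both a reason for its threshold and a range of days, and the two disagree for one scheduled visit. The reason covers missed visits that span the change of interval. The range also covers a previous scan at Week 48, after which every interval is 12 weeks.

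A program written from the condition would give the Week 48 scan 26 weeks. A program written from the day range would give it 22 weeks, and would treat one missed scan as two. Some progressions and deaths that the base rule counts as events would then be censored at Week 48. In addition, Day 344 is exactly Week 49, so it falls under both rule 3 and rule 4.

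**Working it through.** **Inputs.** Scan schedule and window from Protocol Table 1 and SAP 3.1; thresholds and day ranges from SAP 3.3.1. Study day = 7 x week + 1, which matches the SAP (7 x 39 + 1 = 274; 7 x 49 + 1 = 344).

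**Reproducing the SAP's thresholds.** Threshold = (second next scheduled visit - previous visit) + 1 week for an early scan + 1 week for a late scan, with only the late week added from baseline.

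| Previous scan | Window (days) | Next two visits | Formula (weeks) | SAP by day range (weeks) |
|---|---|---|---|---|
| Baseline | - | 8, 16 | 16 + 1 = 17 | 17 |
| Weeks 8 to 32 | before Day 274 | two 8-weekly | 16 + 2 = 18 | 18 |
| Week 40 | 274-288 | 48, 60 | 20 + 2 = 22 | 22 |
| **Week 48** | **330-344** | **60, 72** | **24 + 2 = 26** | **22** |
| Week 60 on | from 414 | two 12-weekly | 24 + 2 = 26 | 26 |

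All four SAP figures reproduce. The only mismatch is Week 48.

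**One missed scan, progression at the next.** All 15 x 15 = 225 day pairs inside the windows were compared with the threshold, counting a gap as two missed visits when it is strictly longer.

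- Week 40 to Week 60: shortest gap 414 - 288 = 126 days, longest 428 - 274 = 154. Pairs above 154 days (22 weeks): 0 of 225.
- Week 48 to Week 72: shortest gap 498 - 344 = 154 days, longest 512 - 330 = 182. Pairs above 154 days: 224 of 225. Pairs above 182 days (26 weeks): 0 of 225.
- For previous scans at Weeks 8 to 40 and 60 to 84, 0 of 225 pairs exceed the SAP's threshold. Week 48 is the single anomaly.

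**Deaths.** After an on-time Week 48 scan (Day 337) with no later evaluable scan, deaths from Day 337 + 155 = 492 to Day 337 + 182 = 519 are censored under the day range and are events under rule 4.

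**With the boundary moved to Day 329/330.** One missed scan: 0 of 225 pairs censored for every previous scan from Week 8 to Week 84. Two missed scans: all 225 pairs are still censored (for example Week 40 to Week 72, 210-238 days against 154; Week 48 to Week 84, 238-266 days against 182).

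**Illustrative size.** The documents give no event or missed-scan rates, so these were assumed: exponential progression with median 200-450 days, exponential death with median 700-1100 days, and 5-20% of scans missed independently. Only the rule 3/4 boundary differed between the two analyses.

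- Events lost per 102 patients: 0.2-0.8 with 6-30 months' follow-up; 0.4-1.5 with 18-36 months.
- PFS6: no change. PFS12: at most 0.15 percentage points. Median PFS: at most 2.3 days.
- Upper quartile of PFS in simulated trials of 102: changed in 1-49% of trials depending on the setting, in either direction (5th to 95th percentile of the shift at most -19 to +84 days).
- DoR was not quantified.

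**The case against.** The strongest reply is that rule 3 states its days outright and can be programmed as written, so apart from Day 344 a programmer has no choice to make. That is fair as a description: the defect can be seen as a misplaced cut-point. It does not rescue the rule, because the range then contradicts the rule's own condition and derivation, and it censors after one missed visit, against the base rule in both documents. Nor is the averaging a harmless simplification at Week 48: the SAP justifies it only for gaps that span the change of interval.

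Several limits stand:

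- The fit to Week 40 alone holds for scheduled scans. An off-schedule scan on Days 289-329 could also be followed by missed Weeks 48 and 60.
- The 225-pair counts assume in-window scans and a strict comparison. The SAP does not say whether a gap equal to the threshold counts; if it does, the one Week 48 pair at exactly 154 days is censored too.
- SAP 4.1.4.2 assigns out-of-window scans to the closest visit, so a scan on Days 310-329 belongs to Week 48 but would keep 22 weeks after the boundary moves. For example, a scan on Day 325 and progression on Day 505 are 180 days apart, above 154. Early out-of-window scans meet the same problem at other boundaries.
- Not all the deaths are wrongly censored. The Week 72 window closes on Day 512, so deaths on Days 513-519 do follow two missed visits.
- The consequence is small, and the endpoint is a descriptive secondary one in a single-arm safety study.

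**Conclusion.** The concern holds as a minor error. For a previous scan in the Week 48 window, rule 3's day range gives 22 weeks where its own reasoning and the SAP's formula give 26, and no other part of either document resolves this. The calendar result depends only on the scan schedule, in-window scans and a strict comparison.

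What is at stake is the tail of the PFS curve, the planned upper quartile of PFS, and DoR through its shared end date. PFS6, PFS12, median PFS and the primary safety endpoint are essentially unaffected. The event counts and quartile shifts rest on assumed rates and show scale only. Whether any patient is affected is not established, nor is which reading was programmed.

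**What to change.** In SAP 3.3.1, end rule 3 at Day 329 (previous assessment on Days 274 to 329, 22 weeks) and have rule 4 apply when the previous assessment is on Day 330 or later (26 weeks). This follows the SAP's own convention of starting a rule when a visit window opens, as Day 274 does for Week 40, and it removes the Day 344 overlap. Change the matching line in the PFS and DoR program.

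The cost is one day boundary and one program line, with no new data. The same edit could state whether a gap must exceed the threshold or only reach it, and how the rule treats out-of-window scans that SAP 4.1.4.2 assigns to a neighbouring visit.

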### **3.3.2 Overall Survival**

The OS is defined as the time from the date of first dose of durvalumab until death due to any cause.

- OS (days) = (date of death or censoring) – (date of first dose of durvalumab) + 1

Any patient not known to have died at the time of analysis will be censored at the last recorded date at which the patient was known to have been alive.

The date that an individual patient was last known to be alive will be identified exclusively using the data recorded within the SURVIVE and DEATH modules of the eCRF.

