- ^b WHO/ECOG PS should also be collected at other site visits that the patient attends if appropriate site staff is available to collect such information. In addition, WHO/ECOG PS should be provided when information on subsequent anticancer therapy is provided, where possible.
- ^c Details of any treatment for NSCLC post the last dose of IP must be recorded in the eCRF. At minimum, collect the start date and description of the subsequent anticancer therapy.
- ^d For patients who discontinue the IP following disease progression, available readings of CT/MRI from local practice should be collected from patients' medical charts while information on subsequent anticancer treatment is collected.
- ^e Patients who decline to return to the site for evaluations should be contacted by telephone as an alternative. In addition to the regularly scheduled survival follow-up, patients may be contacted or the patient's family, or by contact with the patient's current physician in the week following data cutoff to confirm survival status. Every effort should be made to contact patients by telephone to follow and record survival status.
- ^f Free T3 or free T4 will only be measured if TSH is abnormal or if there is clinical suspicion of an AE related to the endocrine system.
- ^g **CCI** [REDACTED].
- ^h Only for patients yet to progress, RECIST 1.1 assessments will be performed on images from CT (preferred) or MRI, each preferably with IV contrast, of the chest and abdomen (including the entire liver and both adrenal glands). Additional anatomy should be image-based on signs and symptoms of individual patients. For patients who are clinically stable and being treated through radiological progression, the follow-up scan performed after a RECIST 1.1-defined PD should be performed preferably at the next (and no later than the next) scheduled imaging visit, and no less than 4 weeks after the prior assessment of PD; special Confirmation of Radiological Progression criteria apply for tumor assessments on the follow-up scan ([Appendix F](#)). If an unscheduled assessment was performed and the patient has not progressed, every attempt should be made to perform the subsequent assessments at their scheduled visits. The modality of tumor assessment should be the same throughout the study.

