6.1.2 Dose and treatment regimens

6.1.2.1 Durvalumab monotherapy

All patients will receive 1500 mg durvalumab via IV infusion q4w for 12 months (13 doses/cycles), starting on Week 0. The last administration of durvalumab will be on week 48 unless there is clinical progression, RECIST 1.1-defined radiological progression, unacceptable toxicity, withdrawal of consent, or another discontinuation criterion is met. See [Figure 2](#). (Please note, if a patient's weight falls to 30 kg or below, the patient should receive weight-based dosing equivalent to 20 mg/kg of durvalumab q4w after consultation between Investigator and Study Physician, until the weight improves to > 30 kg, at which point the patient should start receiving the fixed-dosing of durvalumab 1500 mg q4w).

The durvalumab infusion time is 1 hour \pm 10 minutes; however, if there are interruptions, the total allowed time must not exceed 8 hours with the infusion back maintained at room temperature, otherwise a new dose must be prepared from new vials.

Figure 2 Durvalumab monotherapy dosing schedule

		Durvalumab 1500 mg dose q4w					
Cycle	Week	↓	↓	↓	↓	↓	↓
		1	2	3	4	5 to 13 or PD ^a (12 months)	
		0-3	4-7	8-11	12-15	q4w \pm 3 days until 48 weeks	

PD = Progression of disease; q4w = Every 4 weeks.

^a Or until discontinuation of study drug due to any of the reasons listed in Section [7.1](#).

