7.2 Lost to follow-up

Patients will be considered lost to follow-up only if no contact has been established by the time the study is completed (see Section [4.4](#)), such that there is insufficient information to determine the patient's status at that time. Patients who refuse to continue participation in the study, including telephone contact, should be documented as "withdrawal of consent" rather than "lost to follow-up." Investigators should document attempts to re-establish contact with missing patients throughout the study period. If contact with a missing patient is re-established, the patient should not be considered lost to follow-up and evaluations should resume according to the protocol.

In order to support key end points of PFS and OS analyses, the survival status of all patients in the full analysis and the safety analysis sets should be re-checked, this includes those patients who withdrew consent or are classified as "lost to follow-up."

- Lost to Follow-up – site personnel should check hospital records, the patients' current physician, and a publicly available death registry (if available) to obtain a current survival status. (The applicable CRF modules will be updated.)
- In the event that the patient has actively withdrawn consent to the processing of their personal data, the survival status of the patient can be obtained by site personnel from publicly available death registries (if available) where it is possible to do so under applicable local laws to obtain a current survival status. (The applicable CRF modules will be updated.)

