8.1.1 Survival assessments

[figure not shown]
Assessments for survival must be made as shown in [Table 2](#). Survival information may be obtained via telephone contact with the patient or the patient's family, or by contact with the patient's current physician. The details of first and subsequent therapies for cancer, after discontinuation of treatment, will be collected.

In addition, patients on treatment or in survival follow-up will be contacted following the DCO for the primary analysis and all subsequent survival analyses to provide complete survival data. These contacts should generally occur within 7 days of the DCO.

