### **1.2.3 Overall Survival Assessments**

All patients in the study should be followed up for survival at months 2, 3, 4, 6, 8, 10, and 12 following treatment discontinuation or completion, and then every 12 weeks until death, withdrawal of consent, or the end of the study.

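### The SAP takes the last-known-alive date for OS from two eCRF modules only, so a patient lost around treatment and not traceable can be censored earlier than other records show

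*SAP*

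**What the plan says.** Protocol 9.4 has a patient not known to have died "censored based on the last recorded date on which the patient was known to be alive", and does not say which records may supply that date. SAP 3.3.2 keeps this rule in nearly the same terms but adds that the date will be "identified exclusively using the data recorded within the SURVIVE and DEATH modules of the eCRF".

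Survival status has its own row only in the follow-up schedule (protocol 1.1, Table 2). Table 1, which covers screening and treatment, has none. SAP 1.2.3 agrees: patients are "followed up for survival at months 2, 3, 4, 6, 8, 10, and 12 following treatment discontinuation or completion", then every 12 weeks. On dosing, protocol 6.1.2.1 states: "The last administration of durvalumab will be on week 48", unless treatment stops sooner.

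The protocol adds two safeguards:

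- Section 8.1.1: "patients on treatment or in survival follow-up will be contacted following the DCO for the primary analysis" and for later survival analyses, generally within 7 days. Table 2 footnote e likewise allows contact "in the week following data cutoff to confirm survival status".
- Section 7.2: "the survival status of all patients in the full analysis and the safety analysis sets should be re-checked", including patients who are lost or withdrew consent. For lost patients, sites check hospital records, the current physician and death registries. Where consent to data processing was withdrawn, only public death registries are named. The CRF is then updated.

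The SAP does not say which date applies to a patient with no SURVIVE record.

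**The concern.** During treatment, the evidence that a patient is alive sits in dosing, laboratory, vital-sign and scan records. The SAP rule shuts these out and relies on forms that are not scheduled in that period. For a patient who disappears on treatment, or in the 2 months after it, and whom neither safeguard reaches, up to about a year of documented survival can drop out of the OS analysis.

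Three consequences follow:

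- **OS and OS12.** Event-free time is lost while recorded deaths still count. There is no control arm in which such an artefact might cancel.
- **Coherence with PFS.** SAP 3.3.1 censors PFS at the last evaluable tumor assessment, so one patient could have an OS time shorter than the PFS time.
- **Time to NSCLC-related death.** SAP 3.3.6 uses the date last known alive without naming a source, so the two mortality endpoints could be censored on different dates in the same patient.

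SAP 4.4.2 tabulates patients lost to follow-up and patients who withdrew consent, so the plan expects some.

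**Working it through.** **Plan's own figure.** The documents give no event count, power or loss rate for OS, so there is nothing to reproduce.

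**Schedule.**

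- Thirteen doses every 28 days: last dose on Day (13 − 1) × 28 + 1 = 337, which is week 48.
- First scheduled survival status 2 months (61 days) later: Day 337 + 61 = 398. With the 1-week window, the earliest is Day 398 − 7 = 391.
- OS12 is read at Day 365 (SAP 4.4.2). A patient who completes treatment therefore has no scheduled survival form before the landmark.
- A patient who stops early has the first one 2 months after the last dose. Only loss before that contact leaves no scheduled record.

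**PFS against OS.** A patient lost after an evaluable week 40 scan has PFS censored near Day 40 × 7 + 1 = 281. With no SURVIVE record, the OS date is undefined or earlier.

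**Direction.** Kaplan-Meier survival is the product of (1 − d/n) over death times. Taking living patients out of n too early enlarges each step. With 102 at risk, one death is a step of 1/102 = 0.98%. If ten living patients have been removed at Day 1, it is 1/92 = 1.09%. The curve is lower than with censoring at last contact.

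**Size.** Kaplan-Meier simulation, 1,500 replicates per setting:

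- From the documents: N = 102; loss possible up to Day 337; minimum follow-up 183 days, matching a primary cutoff 6 months after the last first dose; true OS12 of 74.6% and 83.1%, the PACIFIC rates quoted in protocol 2.3.1.
- Assumed: true OS12 of 60% as a lower value; exponential survival; follow-up uniform over 183 to 1,100 days; loss uniform over Days 1 to 337 and unrelated to prognosis; 2%, 5%, 10% or 20% lost and untraceable; Day 1 censoring of those patients as the worst case.

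OS12 with Day 1 censoring minus OS12 with last-contact censoring, in percentage points:

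| True OS12 | 2% lost | 5% lost | 10% lost | 20% lost |
|---|---|---|---|---|
| 60% | −0.2 | −0.6 | −1.3 | −2.7 |
| 74.6% | −0.2 | −0.5 | −1.0 | −2.1 |
| 83.1% | −0.1 | −0.3 | −0.7 | −1.6 |

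Median OS at 10% lost falls from 497 to 480 days (true OS12 60%) and from 868 to 846 days (74.6%).

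**Informative loss.** With 10% lost and the death hazard tripled after loss, true OS12 is 72.8%. Last-contact censoring gives 74.7% and Day 1 censoring 73.8%. Both lie above the truth.

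**Value of the cutoff contact.** If there were no such contact, and patients without a scheduled survival form were set to Day 1 (treatment durations assumed), OS12 would fall by about 1.3 to 2.2 points. Protocol 8.1.1 prevents this.

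**The case against.** The case against is substantial.

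- **The safeguards reach further than Table 1 suggests.** A reader might infer from the missing row that everyone on treatment at the cutoff, or lost during treatment, has no survival data. The documents do not support that. Section 8.1.1 names patients on treatment, and 7.2 sends sites after lost and withdrawn patients and updates the CRF. Section 7.1.3 allows modified follow-up by telephone, relatives, physicians or records, and 7.3 continues survival follow-up after withdrawal unless it is expressly refused. This stands, and it confines the problem to a residual group.
- **Day 1 is not in the OS rule.** The SAP specifies it for PFS only, and the eCRF is not among the documents. If SURVIVE captures an alive date on treatment or at withdrawal, the effect shrinks. This stands: Day 1 is a bound, not a prediction.
- **The effect is small beside the sampling error.** Ignoring censoring, the 95% half-width at OS12 of 74.6% is 1.96 × √(0.746 × 0.254 / 102) = 8.4 points, against a worst-case drop of 1.0 point at 10% lost. OS is a descriptive secondary endpoint. This stands too.
- **Choosing a source is a normal SAP task.** That is true, but this choice excludes valid evidence for the period in which the chosen forms are not scheduled, and leaves no fallback. Here the objection fails.

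Nor do the safeguards close the gap entirely. For a patient who withdrew consent to data processing, a registry can report a death, but the absence of an entry is not a dated contact with a living patient. Deaths can be found while event-free time is lost. The simulation does not include this asymmetry.

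**Conclusion.** The point holds for a limited group: patients lost or withdrawn on treatment, or before the first survival contact after it, who cannot be traced or for whom only registries may be used. For them the SAP rule, followed as written, can set an OS censoring date earlier than other eCRF dates prove, and earlier than their own PFS censoring date.

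If loss is unrelated to prognosis, this lowers OS and OS12 relative to last-contact censoring. Under the assumed worst case the drop in OS12 is about 0.1 to 1.3 points for 2% to 10% affected and up to 2.7 points at 20%. The loss rates, the exponential model and Day 1 censoring are assumptions; the documents give none of them for OS.

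A reader might go further and conclude that OS in this trial is biased downward. The documents do not show that. The actual loss rate and the content of the SURVIVE form are unknown, and with informative loss the estimate can still exceed the truth. In that case last-contact censoring lies further above it. The argument for change is fidelity to the protocol's definition and coherence across endpoints, not a demonstrated large bias.

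**What to change.** In SAP 3.3.2, define the last-known-alive date as the latest non-imputed date, capped at the data cutoff, on any eCRF form that shows the patient alive: SURVIVE or DEATH, dosing, visit, vital signs, laboratory, scan or PRO. This also settles the date for a patient with no SURVIVE record. Excluding imputed dates matters because SAP 4.1.3 imputes partial dates for adverse events and medications.

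Refer to the same date in SAP 3.3.6, so that OS and time to NSCLC-related death are censored alike.

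The cost is SAP wording and minor programming. No new data are collected and no other endpoint changes.
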